## **5 STUDY PROCEDURES AND SCHEDULE OF EVENTS**

### **5.1 Enrollment**

Targeted enrollment is 150 subjects for this study. Study length is 2 years. Subjects will be assigned to 3T or 7T magnet to maintain a balance within the subgroups (primary with or without prior treatment and metastatic with or without prior treatment).

A subset of 25 of the 150 subjects will only undergo MRIs on the 7T magnet. We have recently performed upgrades to the magnet and need to test these new upgrades in order to get the best images to compare with the 3T magnet in the remaining subjects.

### **5.2 Subject Registration**

- 5.2.1 Informed consent will be obtained, refer to section 8.2.
- 5.2.2 New subject registrations will be submitted to the study coordinator, who will record study data on all patients entered into the study and complete subsequent forms.
- 5.2.3 A subject's tumor type (primary versus metastatic) and prior treatment status (yes or no) determine to which of four strata the subject will be assigned. Subjects will be assigned to either 3T or 7T groups in an effort to keep the subgroups balanced and/or possibly depending on MRI availability. We expect up to 20% of subjects will not be able to complete the imaging at the assigned magnet strength and, further, that the proportion may be somewhat higher in those assigned to the 7T magnet (as this magnet is more likely to not be available due to technical and, more rarely, subjects may not be able to tolerate the more confined space). This approach is designed to, as well as possible, maintain balance between the 3T and 7T subgroups .

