**5.3.4 Day 2**

Imaging

- Anatomical imaging on 3T & 7T and dynamic MRI (with ferumoxytol, see section 4.2). A subset of 25 of the 150 subjects will only undergo MRIs on the 7T magnet.
- Dynamic imaging will be performed on the same scanner as on which the dynamic the dynamic imaging was acquired on Day 1(as described below on Section: 6.0). Ferumoxytol Administration:
  - The ferumoxytol will be diluted 1:2 to make a 10mg/ml solution. The dose of ferumoxytol will be 4 mg/kg (to a maximum of 510 mg), and will be administered intravenously on day 2.
  - Dose 1: Give 1/4th of the total dose (1mg/kg); inject at up to 3 ml/sec followed by a saline flush. This rate is required for adequate signal change during the dynamic imaging.
  - Dose 2: Give 3/4th of the total dose (3mg/kg); inject no faster than 1 ml/sec and followed by a saline flush
  - 
  - The dilution and injection parameters of the ferumoxytol may be adjusted to obtain optimal signal changes on MRI/MRA and to decrease the possibility of an allergic reaction. Injection rate can be varied based on the participant's IV site, but the total dose will never exceed 510mg.

Monitoring

- A clinical examination will be performed before and after the MRI session on Day 2.. Blood pressure and pulse will be monitored before the first dose of ferumoxytol and after each dose of ferumoxytol, and at 30 minutes after the initial dose of ferumoxytol.

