### **6 IMAGING SCHEMA AND ACQUISITION**

#### **6.1 Schema**

##### **Day 1**

1. Standard precontrast anatomical MRI sequences at 3T and/or 7T: sagittal T1, coronal FLAIR, MPRAGE, axial T1, T2, T2\*, PD weighted images and DWI.
2. TOF angiography
3. Quantitative T1 images
4. DSC MRI (T2\* weighted) for perfusion with Gd bolus administration dose: 0.1mmol/kg)
5. Quantitative T1 images for permeability measurement will be performed 4 times
6. TOF angiography (postgadolinium)
7. Standard postgadolinium imaging at 3T and 7T: MPRAGE, axial T1, T2, T2\* weighted images.

A subset of 25 of the 150 subjects will only undergo MRIs on the 7T magnet.

[Section 6.1 and 6.2 numbers 4 and 5 will be assigned to either 3 or 7 Tesla. 1, 2, 3, 6 and 7 will be performed on both magnet fields, the order of the scanners will be balanced, see Study Procedures section 5.2.3.] In subjects who cannot tolerate long MRI study either 3T or 7T (MRI with no dynamic imaging) pre-contrast sequences 1, 2 and 3 maybe acquired on Day 2 (dash line in the figure below).

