### **9.3 Descriptive Statistical Analyses**

All analyses described are viewed as descriptive in nature to better understand the variation in these parameters and not to provide definitive results as would be expected in a Phase III trial. The statistical analyses provide appropriate frameworks for assessing the relative magnitudes of effects while potentially controlling for other parameters of interest. Results will be used to plan for future definitive studies of the parameters that have appropriate power calculations and sample sizes. These analyses will be performed when target sample sizes are achieved and not on as interim analyses.

For Primary Aim 1, the primary descriptive comparisons are paired sample t-tests comparing the normalized signal intensity changes (CNR) for T1-weighted MRI signal at 3T and at 7T. Secondary analyses will use a repeated measures analysis of variance (ANOVA) model to compare 3T and 7T while adjusting for other factors including tumor type, prior therapy, and, potentially, important baseline factors that differ between the subjects assigned to the two field strengths. These tests are descriptive in nature and are not powered to provide a complete answer. Subjects who are scheduled to be imaged by a magnet of one field strength but are “crossed-over” to the other magnet or who otherwise fail to complete the scheduled imaging will not be included in these analyses. For the baseline characteristics, if two-sample tests of hypotheses indicate a significant difference ( $p<0.10$ ) between 3T and 7T signal intensity changes for a particular variable, that variable will be included in the ANOVA model as a covariate. Normality will be assessed graphically and, if needed, a transformation (e.g. the logarithmic transform) will be applied. These analyses will be performed for Gd T1-weighted MRI data only

For Primary Aim 2, the analyses will be similar to those for Aim 1 above using normalized (CNR) signal intensity decreases in the DSC data sets. . The same factors and analyses will be used. This objective assesses only Ferumoxytol.

For the first Secondary Aim, mixed model repeated measures ANOVA's will be fit. The outcomes will be relevant dynamic MRI (DCE and DSC) signal intensity changes for permeability and for perfusion. Factors will include imaging agent (Gd or ferumoxytol)

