#### **9.5 Schema to maintain balance between 3T and & 7T groups**

Subjects will be assigned to a subgroup (with or without prior treatment) and will be assigned to undergo dynamic MR imaging at either 3T or 7T in an attempt to balance the subgroup. We expect up to 20% of subjects will not be able to complete the imaging at the assigned magnet strength and, further, that the proportion may be somewhat higher in those assigned to the 7T magnet (as this magnet is more likely to not be available due to technical and, more rarely, subjects may not be able to tolerate the more confined space. This approach is designed to, as well as possible, maintain balance between the 3T and 7T groups with respect to tumor type and prior treatment. This schema is not intended to provide the same validity as randomization within a Phase III trial as this is an exploratory study and not a definitive trial.

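### Assignment to 3T or 7T dynamic imaging follows no stated rule and has no random element, so the between-subject field-strength comparison is open to selection bias

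*Combined protocol and SAP*

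**What the plan says.** Section 5.2.3 says that tumor type and prior treatment "determine to which of four strata the subject will be assigned". It continues: "Subjects will be assigned to either 3T or 7T groups in an effort to keep the subgroups balanced and/or possibly depending on MRI availability". Sections 5.1, 5.2.3 and 9.5 contain no list, algorithm, random element or concealment step, and they name nobody as responsible for the assignment. Section 9.5 is titled as a schema but describes an aim and not a procedure. It acknowledges the limitation: "This schema is not intended to provide the same validity as randomization within a Phase III trial".

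On what is assigned, section 6.1 says of the bolus perfusion series and the repeated T1 series that "numbers 4 and 5 will be assigned to either 3 or 7 Tesla". Section 5.3.3 puts Day 1 dynamic imaging on one magnet according to group. Section 5.3.4 adds for Day 2: "Dynamic imaging will be performed on the same scanner as on which the dynamic the dynamic imaging was acquired on Day 1".

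On analysis, section 9.3 says "the primary descriptive comparisons are paired sample t-tests comparing the normalized signal intensity changes (CNR" at the two field strengths. It offers an adjusted ANOVA as a secondary analysis and excludes subjects who are crossed over or do not complete the scheduled imaging.

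**The concern.** Both primary aims carry a directional hypothesis: better contrast agent detection at 7T in 1.1.1 and higher CNR at 7T in 1.1.2. If each subject has dynamic imaging on one magnet, the contrast between magnets is also a contrast between two groups of patients. An assignment with no stated rule, which may follow scanner availability, does not guarantee that those groups are alike.

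Balancing on tumor type and prior treatment does not by itself balance tumor size, permeability, steroid use or performance status. The plan treats these as relevant. Section 1.1 asks how tumor size and permeability affect the imaging measures, section 2.1 says steroids and other treatments alter tumor vasculature and permeability, and 9.2 lists all four as baseline variables. Eligibility is wide (any point in treatment, ECOG up to 3), so there is room for the groups to differ. Section 9.3 says the results will be used to plan later definitive studies, so a biased difference would carry forward into them.

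**Working it through.** **Step 1. Is the comparison between subjects?**
- Sections 5.3.3 and 6.1 put the Day 1 dynamic series on one magnet, by group.
- Section 5.3.4 puts the Day 2 dynamic series on that same magnet.
- Section 5.6 counts a subject as evaluable for an aim only if imaged on the assigned magnet that day.
- Section 9.3 itself speaks of baseline differences between the subjects assigned to each field strength, and of two-sample tests.

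These agree: within a visit there is no 3T/7T pair of dynamic measurements. Two other statements in section 9 do not fit: the paired t-test, and the statement for the first secondary aim that each subject supplies a measure for every combination of agent and field strength.

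**Step 2. Inputs.** The plan has no figure of its own to reproduce: 9.4 says the sample size has no statistical justification, and no alpha, power, effect or SD is given for the primary comparisons.
- Enrolment 150 (5.1, 9.4); 7T-only subset 25 (5.1); loss from the assigned magnet up to 20% (5.2.3, 5.6).
- Assumed: the 25 stay out of the comparison (the documents do not say), 1:1 split, two-sided 5% test, normal approximation, bias b in units of the outcome SD.

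Subjects left: (150 − 25) × 0.80 = 100, or 50 per group. SE = √(1/50 + 1/50) = 0.20 SD.

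**Step 3. False-positive rate under no true difference.** Rate = Φ(b/SE − 1.96) + Φ(−b/SE − 1.96).
- b = 0: 5.0%.
- b = 0.1: Φ(−1.46) + Φ(−2.46) = 7.9%.
- b = 0.2: Φ(−0.96) + Φ(−2.96) = 17.0%.

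Over other readings of the sample size:

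| Basis | Per group | SE (SD) | b = 0.1 | b = 0.2 |
|---|---|---|---|---|
| 125, 20% loss | 50 | 0.200 | 7.9% | 17.0% |
| 150, 20% loss | 60 | 0.183 | 8.5% | 19.5% |
| 125, no loss | 62.5 | 0.179 | 8.6% | 20.1% |
| 150, no loss | 75 | 0.163 | 9.4% | 23.2% |

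More subjects do not help, because the bias stays while the standard error shrinks.

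**Step 4. What would produce such a bias?** Bias = imbalance × effect. A binary factor worth 1 SD of CNR, with prevalence 10 or 20 points apart between groups, gives 0.1 or 0.2 SD. A factor worth 0.5 SD with a 10-point gap gives 0.05 SD and a rate of 5.7%. All of these are assumptions.

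**Step 5. Would the 9.3 covariate screen catch it?** Suppose the p<0.10 screen is a test of baseline difference. At 50 per group, a continuous factor must then differ by more than 1.645 × 0.20 = 0.33 SD to enter. A 0.3 SD difference gives z = 0.3/0.20 = 1.5 and is missed. With an assumed correlation of 0.3 to 0.5 with CNR, it leaves 0.3 × 0.3 = 0.09 to 0.3 × 0.5 = 0.15 SD of bias. Larger imbalances in measured factors would enter, but only in the secondary model.

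**The case against.** The strongest reply is that this is a disclosed choice. Section 9.5 says the scheme lacks the standing of randomization, and 9.3 calls every analysis descriptive. The plan also collects the factors of concern (9.2) and adjusts for tumor type, prior therapy and differing baseline factors, for both aims (9.3). That stands in part: the limitation is not hidden, and large imbalances in measured factors would be handled. But disclosure does not remove bias, the primary comparison is unadjusted, and unmeasured factors stay outside the model.

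A second reply is that the comparison may be paired after all. Section 6.1 has pre- and post-gadolinium T1 imaging on both magnets, so a within-subject T1 CNR for Aim 1 is conceivable, and visits can repeat. If real pairs existed, assignment bias would largely disappear. However, 9.2 ties CNR to the dynamic data sets, 5.6 ties evaluability to the assigned magnet, no section schedules a repeat visit on the other magnet, and the perfusion series for Aim 2 has no second-magnet counterpart within a visit.

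A third reply is that availability may be unrelated to the patient. That stands: in that case the bias would be small.

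A reader might go further and infer that staff choose the magnet predictably and knowing the patient, or that patients who would tolerate the 7T bore poorly are steered to 3T. The documents do not support this. They name no assigner, and they raise bore tolerance as a rarer reason for not completing imaging, not as a basis for assignment. Outside the 7T-only subset, 3T-assigned subjects are also due 7T anatomical scans.

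A reader might also take the opening of 9.5 ("Subjects will be assigned to a subgroup (with or without prior treatment") as a real conflict with the four strata. The same section later names tumor type too, and 5.1 lists all four subgroups, so this is editorial.

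**Conclusion.** The point holds as a risk of avoidable selection bias in the dynamic 3T-versus-7T comparison. It rests on two facts in the documents: no allocation rule or random element is specified, and dynamic imaging is on one magnet per subject within a visit. The size is not known from the documents. The 8% to 17% false-positive range rests on an assumed bias of 0.1 to 0.2 SD, about 50 per group and a two-sided 5% test.

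The problem is bias and not precision. With 50 per group, the difference detectable with 80% power is (1.96 + 0.84) × 0.20 = 0.56 SD, whether or not assignment is random. Randomization would not remove bias from excluding crossed-over subjects, whom the plan expects somewhat more often at 7T.

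**What to change.** In 5.2.3 and 9.5:
- For future subjects outside the 25 in the 7T-only subset, assign 3T or 7T from a computer-generated permuted-block list within the four strata of 5.2.3. Open each assignment after eligibility is confirmed and when both magnets are expected to be available for the visit.
- If only one magnet is available and the visit cannot be moved, assign by availability and record this. Keep the subject in the descriptive summaries, and repeat the 3T-versus-7T comparison in randomly assigned subjects only.
- Keep the 5.6 rule for later failures, record the reason each time, and state that randomization does not protect against excluding those subjects.
- Name the same four strata in the first sentence of 9.5.

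In section 9.3, including its text on the first secondary aim, reconcile the paired t-test and the four-measures-per-subject statement with the one-magnet dynamic schedule.

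The cost is a list and a protocol amendment, with no extra subjects. Most subjects must already be scheduled on both magnets, so the added burden is modest. The downside is some loss of scheduling freedom and possibly a few subjects outside the randomized comparison. The list cannot cover subjects already enrolled, including the eleven feasibility subjects in 9.2.

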### **5.3 Study Visits**

- 5.3.1 Each study visit consists of 3 days. There may be up to 7 days between Day 1 and Day 2 visits. A study visit may be repeated up to four times, but not any more frequently than every 3 weeks.
- 5.3.2 The subject may be given Benadryl before MRI scanning to help with relaxation during the MRI scan and/or to prevent an allergic reaction to the Ferumoxytol. Subject's need for anti-anxiolytics for each MRI study visit will be evaluated and administered as needed. Common anti-anxiolytics include lorazepam and diazepam; diphenhydramine may also be used. The administration of a relaxing/anti-anxiolytic agent will be given at the treating physician or the PI's discretion and is considered routine prior to MRI and as such is not being evaluated on this study.

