### 1.2 Secondary

1.2.1 To describe the blood brain barrier permeability to Ferumoxytol and to a standard gadolinium-based MRI contrast agent using signal intensity changes as described above.

1.2.2 To describe cerebral blood volume (CBV) measurements obtained using a standard gadolinium MRI contrast agent and ferumoxytol. CBV will be quantified using dynamic susceptibility contrast (DSC) techniques with Gd or Ferumoxytol contrast agents. The use of DSC techniques with standard Gd MRI contrast agents in tumors with leaky blood vessels can lead to inaccurate CBV estimates because of Gd extravasation. We expect to obtain lower blood volume estimates with ferumoxytol than with gadolinium in leaky tumors. We do not expect significant differences in less leaky tumors.

1.2.3 To evaluate tumor microvascularity on susceptibility-weighted images (SWI). The susceptibility weighted images will be acquired before and after ferumoxytol administration to investigate blood vessel visibility within the tumor bed. Morphological and caliber differences of intratumoral vessels in comparison to normal cortical penetrating vessels will be analyzed.

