1.2.4 To describe the microscopic distribution of ferumoxytol particles in tissue

## 2 BACKGROUND

### 2.1 The blood-brain barrier in CNS tumors

The BBB is an anatomical feature of CNS capillaries that consists of a continuous layer of endothelial cells bound together with tight junctions that allow very little transcellular or pericellular leakage of blood-borne molecules (5, 36). In normal brain, the BBB limits permeability based on electric charge and lipid solubility, and normally excludes molecules of greater than  $M_r$  180. The neurovascular unit is a new, integrated approach

to thinking about and working with the BBB. It is comprised not only the BBB endothelial cells but also the basement membrane, pericytes, microglia and astrocytic foot processes in the capillary microenvironment. Local environmental and cellular factors and the varying integrity of the neurovascular unit impact barrier permeability in tumors of the CNS, both before and after treatment. Brain tumors often have a leaky blood-tumor barrier (BTB) because the neovasculature in the tumor lacks some BBB characteristics (5). The barrier in the brain around malignant tumors can have variable permeability due to neovascularization, inflammation, and gliosis. The well-vascularized, actively proliferating edge of the tumor is particularly variable and complex in terms of barrier integrity (18, 29, 36).

Cancer treatments such as steroids, chemotherapy, radiotherapy, or anti-angiogenesis therapy induce changes in tumor vasculature, tumor permeability, and tumor cell viability. Many of these effects will occur hours to days after treatment, but changes in gross tumor volume can only be measured at later times (several days to weeks). Methods to measure early anti-tumor effects would be useful in predicting outcomes and modifying therapies to maximize response.

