## 3 SUBJECT SELECTION

### 3.1 Eligibility Criteria

- 1) Subjects with radiographically suspected, histologically or cytologically confirmed primary brain tumors or brain metastasis are eligible.
- 2) Subjects may be enrolled at any point in diagnosis or treatment.
- 3) Subjects must have had radiographically evaluable or measurable disease with standard MR imaging.
- 4) .
- 5) Age  $\geq$ 18 years. Both men and women and members of all races and ethnic groups will be included.
- 6) ECOG performance status  $\leq$  3 (KPS  $\geq$  30).

- 7) Ability to understand and the willingness to sign a written informed consent document, or have a representative able to consent for the subject.
- 8) Sexually active women of child-bearing potential and men must agree to use adequate contraception (hormonal or barrier method of birth control; or abstinence) prior to study treatment and for the duration of study treatment. Should a female become pregnant or suspect she is pregnant while participating in this study, she should inform her treating physician immediately.
- 9) Subject agrees to complete follow up visit.

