### **3.2 Exclusion Criteria**

- 1) Subjects with clinically significant signs of uncal herniation, such as acute pupillary enlargement, rapidly developing motor changes (over hours), or rapidly decreasing level of consciousness.
- 2) Subjects who have a contraindication for MRI: metal in their bodies (a cardiac pacemaker or other incompatible device), are severely agitated, need monitored anesthesia for scanning, or have an allergy to Gd contrast material.
- 3) Subjects with known hepatic insufficiency or cirrhosis
- 4) History of allergic reactions attributed to compounds of similar chemical or biologic composition to ferumoxytol
- 5) Subjects with known or suspected iron overload (genetic hemochromatosis or history of multiple transfusions)
- 6) Subjects expecting to undergo surgery between the imaging sessions. Subjects may undergo surgery at any time before the first, or after the last imaging session. This exclusion only applies to each study visit (3 day scanning session), and does not apply to the time (at least 3 weeks) between each study visit.
- 7) Uncontrolled concurrent illness including, but not limited to, ongoing or active infection, symptomatic congestive heart failure, unstable angina pectoris, cardiac arrhythmia, or psychiatric illness/social situations that would limit compliance with study requirements.
- 8) Pregnant or lactating women are excluded from this study because of possible risk to the fetus or infant.
- 9) Inability or unwillingness to undergo the complete series of imaging sessions. Inability or unwillingness to complete the one month follow-up.
- 10) HIV-positive subjects on combination antiretroviral therapy are ineligible because of the potential for pharmacokinetic interactions with ferumoxytol.
- 11) Subjects with GFR < 50.
- 12) Subjects with three or more drug allergies from separate drug classes.

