## **4 CONTRAST AGENT FORMULATION AND PROCUREMENT**

### **4.1 Gadolinium**

Gadolinium is a standard contrast agent used in clinical practice and will be administered on day 1 as an I.V. bolus of 0.1 mmol/kg at a flow rate of up to 3 mL/s, followed by a saline flush. for dynamic MR imaging followed by routine MR imaging. The appropriate

volumes of contrast agents are based on the patient's weight (0.2 ml/kg gadoteridol + 20ml saline flush).

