#### **4.2 Ferumoxytol**

- 4.2.1 **Agent Accountability:** The Investigator, or a responsible party designated by the Investigator, must maintain a careful record of the inventory and disposition of the study agent.
- 4.2.2 **Availability:** Ferumoxytol is purchased by the investigators from the manufacturer, AMAG Pharmaceuticals, Inc. (Cambridge, MA)
- 4.2.3 **Product description:** Ferumoxytol is a semi synthetic carbohydrate coated ultrasmall superparamagnetic iron oxide particle. The drug is formulated with mannitol; each vial contains 30 mg/mL of iron and 44 mg/mL of mannitol. A dose of 510 mg of iron is 17 mL. Ferumoxytol is isotonic: the osmolality is 270-330 mOsm. The amount of free (BDI) iron for ferumoxytol is approximately six - fold lower than for currently approved parenteral iron products at a similar dose. The product contains no preservatives. The pH is 6 to 9.
- 4.2.4 **Preparation:** The appropriate volume of drug is based on the subject's weight. The drug will be stored at room temperature (68-77 degree Fahrenheit) away from direct sunlight. The solution will be prepared and dispensed by the investigational drug pharmacist. The Ferumoxytol will be injected in the MR suite by either a nurse or technician.

The ferumoxytol will be diluted 1:1 to make a 15mg/ml solution. The total dose of ferumoxytol will be 4 mg/kg (to a maximum of 510 mg), and will be administered intravenously on day 2.

The dilution and injection parameters may be adjusted to obtain optimal signal changes. The total dose will not exceed 4 mg/kg or 510 mg.

See Section 5.3.4 for administration.

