and field strength (3T and 7T). Each subject will contribute one measure for each combination of imaging agent and field strength (4 measures total). This will not be a definitive analysis as the power cannot be determined *a priori*. The mixed model allows for estimation of the means and confidence intervals for imaging agent and field strength (57). These data will be used to plan future comparative studies. For the second Secondary Aim, blood volumes will be compared using repeated measures ANOVA to compare the imaging agents. For the third Secondary Aim, analyses will add covariates of prior therapy to the analyses listed above. For the comparisons between treated and untreated subjects, means and confidence intervals will be estimated for each group for the perfusion and permeability measures and for the baseline characteristics listed above. Since prior treatment is likely confounded with other variables (e.g. disease severity), these comparisons will also be descriptive in nature and mainly be used to plan future studies.

For Secondary Aim five, the pathology will be analyzed qualitatively for the presence of iron staining. The amount and localization of the staining will be assessed, with attention paid to whether the tumor cells themselves or reactive cells in and around the tumor demonstrate iron uptake.

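### Gadolinium always precedes ferumoxytol by up to 7 days, so the secondary agent comparisons also pick up any therapy started or changed in the gap

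*Combined protocol and SAP*

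**What the plan says.** **Order and gap.** Section 4.1 says gadolinium "will be administered on day 1 as an I.V. bolus of 0.1 mmol/kg"; section 4.2 gives the ferumoxytol dose "and will be administered intravenously on day 2". No subject receives the agents in the other order. Section 5.3.1 adds: "There may be up to 7 days between Day 1 and Day 2 visits".

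**Who is studied.** Section 3.1: "Subjects may be enrolled at any point in diagnosis or treatment". The one event that section 3.2 rules out inside a study visit is an operation: "Subjects expecting to undergo surgery between the imaging sessions" are excluded. Drug therapy and radiotherapy have no corresponding rule.

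**What therapy does.** Section 2.1 says that steroids and the main cancer treatments alter tumor vessels and permeability, and on timing: "Many of these effects will occur hours to days after treatment". Section 2.3 names CBV as the outcome for judging how therapy affects tumors.

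**Agent comparisons.** Objective 1.2.1 describes permeability to the two agents. For CBV, objective 1.2.2 states: "We expect to obtain lower blood volume estimates with ferumoxytol than with gadolinium in leaky tumors". In section 9.3 the model for 1.2.1 has agent and field strength as factors, and for 1.2.2 "blood volumes will be compared using repeated measures ANOVA to compare the imaging agents". The only therapy covariate in 9.3 is prior therapy. Steroid use appears in section 9.2 as a baseline summary.

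**The concern.** The agent contrast is a difference between two days as well as between two agents. If a subject starts or changes a vessel-active therapy after the gadolinium scan and before the ferumoxytol scan, the plan has no means of telling the therapy effect from the agent effect. The protocol treats CBV and permeability as quantities that therapy moves on this time scale, and it recruits people at any stage of treatment.

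The agent estimates are meant to inform the design of later comparative studies. A bias of this kind does not shrink as more subjects are enrolled. If therapy in the gap is not captured during the study, it may not be possible to separate the two effects afterwards.

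**Working it through.** The plan states no figure to reproduce. It gives no effect size, SD, alpha or power for the agent comparison, and section 9.4 disclaims any statistical basis for the 150 subjects. The figures below are illustrations on stated assumptions.

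**1. What the contrast estimates.** For subject i, let D_i be the ferumoxytol value on Day 2 minus the gadolinium value on Day 1. Then

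mean of D = true agent effect + f × d,

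where f is the share of subjects with a therapy start or change in the gap and d is the mean therapy effect in those subjects.

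**2. Size of f × d.** Neither input is in the documents. Express d as a percentage of mean CBV, and assume that subjects with a change have average CBV and that all changes act the same way:

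- f = 10%, d = 10%: 0.10 × 0.10 = 1% of CBV.
- f = 30%, d = 30%: 0.30 × 0.30 = 9% of CBV.

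The upper figure takes both assumed maxima at once.

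**3. Does the prior-therapy covariate help?** Prior therapy has the same value on Day 1 and Day 2, so its main effect cancels in D_i. A simulation confirms this (300 runs, 150 subjects, true agent effect 0, assumed f = 0.25 and d = -20 points on a CBV scale of 100; expected bias 0.25 × -20 = -5). The mean agent estimate was:

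- unadjusted: -4.8
- with the prior-therapy covariate: -4.8
- limited to subjects with no therapy change in the gap: +0.2

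The restriction removes the bias to within simulation error; the covariate does not.

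**4. Would interval length as an ordinary covariate help?** No, for the same reason. If L_i is the gap and enters as g × L_i on both days, then g × L_i - g × L_i = 0 in the difference. To act on the contrast it must be an agent-by-interval term or, equivalently, a covariate on D_i.

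**5. What a bias of this size could do.** Assume a two-sided 5% test, a true agent effect of 0, a bias of 5 points and n = 150.

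- SD of D = 30: SE = 30/√150 = 2.45 and 5/2.45 = 2.04, so the chance of p < 0.05 is about 53%.
- SD of D = 50: SE = 50/√150 = 4.08 and 5/4.08 = 1.22, so the chance is about 23%.

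With f = 10% and d = 10 points (bias 1 point), the chances are 6.9% and 5.7%. The effect therefore runs from negligible to material, depending on inputs that only recording can supply.

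**6. Does normalisation help?** Section 7.2.2 divides by a control region. That does not remove a change confined to the tumor.

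**The case against.** The case on the other side is substantial, and much of it stands.

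- **Scope.** Only 1.2.1 and 1.2.2 are affected. Primary Aims 1 and 2 compare 3T with 7T within a single agent, so agent order does not enter them. Section 9.3 labels every analysis descriptive. This stands and limits the weight of the point. It does not excuse an avoidable bias in estimates intended for planning.
- **The order may be unavoidable.** Section 2.2 gives plasma half-lives of 14-30 hours for these coated iron particles, which makes simple counterbalancing difficult. This stands.
- **Seven days is a maximum, and surgery is excluded.** Both are true. It would be wrong to say that the plan has no control over the gap, or that contamination is certain. The surgery rule nevertheless leaves the therapies named in section 2.1 open.
- **Recording.** Case-report forms are not among the documents, so one can say only that the plan does not mention capturing therapy in the gap.
- **Direction.** A reader might infer that the bias favours the study's own hypothesis, because ferumoxytol comes second and is predicted to give lower CBV. The documents do not support that as a general statement. Section 2.1 gives no sign for therapy effects, and it also describes treatment harming the barrier, which could raise leakage. Objective 1.2.1 predicts no direction. Reduced leakage on Day 2 would hardly move ferumoxytol CBV, since section 2.3 expects little first-pass leakage of that agent. Only a true fall in tumor blood volume would mimic the prediction. Objective 1.2.2 also expects no material difference in less leaky tumors, so a shift seen there too would count against it. That is only a partial check.

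**Conclusion.** The confounding is real. With a fixed order, a gap of up to 7 days and no within-gap therapy term, the agent contrasts for 1.2.1 and 1.2.2 contain f × d in full, and the planned covariate cannot remove it. On assumed values of 10-30% for both inputs, the bias is about 1-9% of CBV. The range rests wholly on those assumptions and on changes acting in one direction; mixed directions would give less. The sign is open, and agreement with the 1.2.2 prediction would be spurious only where therapy truly lowers tumor blood volume.

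This is an inexpensive improvement to secondary, descriptive comparisons. It is not a threat to the primary aims.

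**What to change.** 1. **Record**, for each study visit, the Day 1-Day 2 interval and any start, change or ongoing course of steroid, chemotherapy, radiotherapy or anti-angiogenic therapy within it. Ongoing courses matter because a subject partway through treatment has no start or change but may still have a changing tumor.
2. **In section 9.3, for 1.2.1 and 1.2.2**, pre-specify an agent comparison limited to subjects with no such therapy change in the gap, and report it beside the all-subject result. It should not replace that result, because the restriction selects on something that happens after Day 1.
3. **Enter interval length** as an agent-by-interval term, or as a covariate on the paired difference, and state the gap length at which the agent effect is read. A subject-level main effect would leave the contrast unchanged.
4. **Report** the distribution of the interval and the number of subjects with a change, so that f is known.

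The cost is one form item, a few sentences in 9.3, and fewer subjects in the restricted analysis, hence wider confidence intervals there. No change to the visit schedule or to treatment is proposed.
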